7 STATISTICAL ANALYSES

SAS® version 9.2 or higher will be used for statistical analyses, tabulations and graphical presentations. S-Plus®, may also be used for graphical presentations.

7.1 General Methods

Continuous variables will be summarized using descriptive statistics, i.e., medians, minimums, maximums, and means with standard deviations/(or standard errors of the mean). Categorical

variables will be summarized by frequencies and percentages. Percentages will be rounded and may not always add up to 100. Confidence intervals for binomial proportions will be derived using the Clopper-Pearson method.²³

Unless otherwise specified, the following general rules will be applied:

- Data from Part 1 and Part 2 will be combined, with safety and tolerability data summarized by treatment group, and efficacy data summarized by tumor types.
- All results from Part 3 and Part 5 will be included in listing only.
- Additional outputs may be provided for SCCHN participants as appropriate.

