1.3 Objectives

1.3.1 Primary Objective

1.3.1.1 Primary Objective for the Dose Escalation and Cohort Expansion (Part 1; Completed) and the SCCHN Cohort Expansion (Part 2; Completed)

The Dose Escalation and Cohort Expansion (Part 1): To assess the safety and tolerability of lirilumab given in combination with nivolumab and to identify DLTs and the MTD of the combination in subjects with advanced (metastatic and/or unresectable) solid tumors.

The SCCHN Cohort Expansion (Part 2): To assess the safety and preliminary anti-tumor activity of the combination of lirilumab and nivolumab in subjects with advanced solid tumors.

1.3.1.2 Primary Objective for the SCCHN Randomized Cohorts (Part 3 - closed to enrollment)

To estimate the ORR of lirilumab given in combination with nivolumab in subjects with recurrent or metastatic SCCHN that has relapsed or progressed within 6 months of the last dose of a platinum-containing therapy and whose tumors express PD-L1.

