8.2 Population for Analyses

- All Enrolled Data set: subjects who signed informed consent and registered in the study.
- All Treated Data set: all subjects who received at least 1 dose of any study drug.
- Response-Evaluable Data Set: all treated subjects who receive any study drug, have a baseline tumor assessment with measurable disease, and 1 of the following:
 - at least 1 evaluable on-treatment tumor assessment,
 - clinical progression, or
 - death prior to the first on-treatment tumor evaluation.
- Lirilumab PK Data Set: all subjects who receive at least 1 dose of lirilumab and have adequate serum concentration data for lirilumab PK.
- Nivolumab PK Data Set: all subjects who receive at least 1 dose of nivolumab and have adequate nivolumab PK.
- Lirilumab Immunogenicity Data Set: all subjects who receive at least 1 dose of lirilumab and have at least 1 ADA sample available.
- Nivolumab Immunogenicity Data Set: all subjects who receive at least 1 dose of nivolumab and have at least 1 ADA sample available.
- Ipilimumab Immunogenicity Data Set: all subjects who receive at least 1 dose of ipilimumab and have at least 1 ADA sample available.
- Biomarker Data Set: all treated subjects who have biomarker data available.
- For the SCCHN Randomized Cohorts (Part 3), Randomized Subjects Data Set: All enrolled subjects who were randomized. This is the dataset for baseline demographics and efficacy analyses for this cohort.
- For the SCCHN Randomized Cohorts (Part 3), PRO subjects: All randomized subjects with baseline and at least 1 post-baseline PRO assessment.

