8.4.2 Efficacy Analyses

8.4.2.1 The SCCHN Randomized Cohorts (Part 3) Primary Endpoint Analysis

The primary endpoint of ORR in subjects randomized to lirilumab plus nivolumab will be analyzed for the SCCHN Randomized Cohorts (Part 3). Subjects will be enrolled if PD-L1 is expressed in $\geq 1\%$ of tumor cells.

CI_s will be provided separately for each treatment arm using the Clopper-Pearson method.

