8.4.2.2 Secondary Endpoints Analysis

Individual BOR, DOR, and PFS will be listed using RECIST v1.1 criteria. Summary tables will be presented on efficacy endpoints for each randomized treatment arm. The OS and PFS rates at specific timepoints (eg, at 24 weeks) and corresponding CI will be estimated by KM methodology depending on data availability. ORR, DOR and PFS analyses will include subjects in the cohort expansion phase and subjects in dose escalation matching those in cohort expansion by disease type and treatment. Individual changes in the tumor burden over time will be presented graphically within a disease type.

[REDACTED]

The number and percentage of subjects in each category of BOR (CR, PR, SD, PD, or unable to determine) will be presented by treatment arm and/or tumor types, if applicable. Finally, a waterfall plot showing the biggest reduction in the sum of target lesions will be produced for response-evaluable subjects.

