Overall survival (OS) for a subject is defined as the time from date of first dose of study medication to the date of death for any cause. A subject who has not died will be censored at last known date alive. OS for a subject who initiated new cancer treatment, will also be censored at the date of the new treatment initiation.

The efficacy endpoints that will used to evaluate BOR, PFS, and OS include:

- Objective response rate (ORR): The proportion of subjects with BOR of either a CR or PR in the population of interest (all treated patients or response evaluable patients).
- Disease control rate (DCR): The proportion of subjects with BOR of either a CR, PR, or SD in the population of interest (all treated patients or response evaluable patients).
- Median duration of response (mDOR)
- Median time to response (mTTR)

- Median overall survival (mOS)
- Median progression-free survival (mPFS)
- Progression-free survival rate (PFSR) at Month 3, 6, and 12: The proportion of subjects remaining progression free and surviving at 3, 6, 9, and 12 months (conditional on availability of a minimum number of subjects with sufficient follow-up) calculated by the product-limit method (Kaplan-Meier estimate)
- Overall survival rate (OSR) at Month 6, 12, 18, 24, and 36: The proportion of subjects surviving at month 6, 12, 18, 24, and 36 (conditional on availability of a minimum number of subjects with sufficient follow-up) calculated by the product-limit method (Kaplan-Meier estimate)

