6.3 Populations for Analyses

- All Enrolled Subjects: All subjects who signed an informed consent and were registered into IRT;
- All Treated Subjects: All subjects who have received at least one dose of study medication;
- Response-Evaluable Subjects: All treated participants with measurable disease at baseline and one of the following: 1) at least one post-baseline tumor assessment, 2) clinical progression, or 3) death
- All Randomized Subjects: all subjects who were randomized in Part 3. This population will be used for listing of randomization schedule for Part 3 only.
- Lirilumab PK: all subjects who receive at least 1 dose of lirilumab and have adequate serum concentration data for lirilumab PK.
- Nivolumab PK: all subjects who receive at least 1 dose of nivolumab and have adequate nivolumab PK.
- Lirilumab Immunogenicity: all subjects who receive at least 1 dose of lirilumab and have at least 1 ADA sample available.
- Nivolumab Immunogenicity: all subjects who receive at least 1 dose of nivolumab and have at least 1 ADA sample available.
- Biomarker: all treated subjects who have biomarker data available.

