7.5 Efficacy

Efficacy analyses based on Response-evaluable Participants may be performed as supportive analyses. If majority of All Treated Participants is included in Response-evaluable Participants, limited efficacy analyses will be performed on Response-evaluable Participants (eg, ORR). For interim analyses when the minimum follow-up period is less than sufficient to warrant adequate interpretation of the result, efficacy analyses may be performed on Response-evaluable Participants.

Time to event distribution (e.g. progression free survival, overall survival, and duration of response) will be estimated using Kaplan-Meier (K-M) method. When appropriate, the median along with 95% CI will be provided using Brookmeyer and Crowley methodology²⁴ (using log-log transformation for constructing the confidence intervals). Rates at fixed timepoints (e.g. PFSR at 6 months or OS at 12 months) will be derived from the K-M estimate and corresponding confidence interval will be derived based on the Greenwood formula using log-log transformation²⁵. Confidence intervals for binomial proportions will be derived using the Clopper-Pearson method.

In general, efficacy summaries will be provided by tumor type and treatment group.

Summary:

- ORR and DCR with corresponding 2-sided 95% CI, together with breakdown of BOR
- Duration of response, OS, and PFS with median (95% CI) and range (min, max) by K-M method. The number of subjects still in response at the time of data lock will be indicated
- Time to response with median (95% CI) and range (min, max) by K-M method

Figure:

- Maximum reduction in baseline target lesions (aka waterfall plot)
- Kaplan-Meier (K-M) plot of duration of response for responders only
- Swimmer plot of time to response and duration of response, including time on therapy for responders only
- K-M plot of PFS
- K-M plot of OS

Listing:

The following will be listed by tumor type and treatment group.

- By patient listing of all tumor lesion measurements by visit
- By patient listing of tumor evaluation at each visit
- Subject level efficacy for all treated subjects: tumor best overall response (BOR), maximum reduction in tumor burden from baseline, time to response, duration of response, time to progression, and death indicator

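### The SAP puts Part 3 in listings only, while the current protocol requires an ORR interval and efficacy tables for each randomized arm; the SAP's own Part 3 ORR estimate has no analysis behind it

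*SAP*

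**What the plan says.** **Protocol (Revised Protocol 12).** The Part 3 primary objective in 1.3.1.2 is "To estimate the ORR of lirilumab given in combination with nivolumab". Of the Part 3 randomized set, 8.2 says: "This is the dataset for baseline demographics and efficacy analyses for this cohort". For the primary endpoint, 8.4.2.1 says that confidence intervals "will be provided separately for each treatment arm using the Clopper-Pearson method". For the other efficacy endpoints, 8.4.2.2 says: "Summary tables will be presented on efficacy endpoints for each randomized treatment arm". None of these statements is conditional.

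**SAP.** Among general rules that apply unless the plan says otherwise, 7.1 states: "All results from Part 3 and Part 5 will be included in listing only". On All Randomized Subjects, 6.3 states: "This population will be used for listing of randomization schedule for Part 3 only". The efficacy section, 7.5, promises "ORR and DCR with corresponding 2-sided 95% CI, together with breakdown of BOR" and does not mention Part 3.

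**Elsewhere in the SAP.** Section 4.1 sets ORR estimation as the anti-tumor endpoint for all Parts. Section 5.4 keeps a final Part 3 ORR analysis about 6 months after the last subject is randomized and treated. The Part 3 text at the end of 4.2.1.4 defines its primary ORR on everyone randomized to the combination arm. The bulleted ORR definition earlier in 4.2.1.4 instead counts subjects with "BOR of either a CR or PR in the population of interest (all treated patients or response evaluable patients").

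**The concern.** Estimating ORR on the combination is the whole of the Part 3 primary objective, and Part 3 holds the study's only concurrent randomized nivolumab arm. A programmer following SAP 7.1 and 6.3 would produce no Part 3 ORR, no interval and no table by arm. Readers of the report would have to count responders from subject listings. They would also have to choose between the two populations that 4.2.1.4 offers, and between the two-sided 0.10 level of 5.4 and the 95% level of 7.5.

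**Working it through.** **Step 1. Requirement against commitment.**

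| Item for Part 3 | Protocol | SAP |
|---|---|---|
| Efficacy population | Randomized set (8.2) | Randomized set used only for the schedule listing (6.3) |
| ORR interval, Arm A | Required (8.4.2.1) | Listing only (7.1) |
| ORR interval, Arm B | Required (8.4.2.1) | Listing only (7.1) |
| Efficacy tables by arm | Required (8.4.2.2) | Listing only (7.1) |

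**Step 2. Does any SAP section make an exception?** The opening of 7.1 allows one. Section 7.5 gives general rules by tumor type and treatment group without naming Part 3. The additional SCCHN outputs in 7.1 are optional. Sections 7.3 and 7.6 limit their summary tables to Parts 1 and 2. No exception is made, so the commitment is 0 of 2 intervals.

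**Step 3. Is the SAP consistent with itself?** No. Sections 4.1, 4.2.1.4 (Part 3 text) and 5.4 call for a Part 3 ORR estimate, and 6.3 and 7.1 withhold it.

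**Step 4. Is the change recorded?** SAP 2.4 ties the plan to the protocol version dated 08-May-2018. SAP 11 records the update to Revised Protocol 12, the removal of central review, and the removal of stratified or sub-population ORR summaries. It does not record listing only.

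**Step 5. What the missing intervals would look like.** The planned sizes are 225 × 2/3 = 150 in Arm A and 225 × 1/3 = 75 in Arm B. For x responders among n subjects, the Clopper-Pearson limits are:

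- lower = Beta quantile at α/2 with parameters (x, n − x + 1)
- upper = Beta quantile at 1 − α/2 with parameters (x + 1, n − x)

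The plan's own figure comes first. Protocol 8.1.4 and SAP 5.4 print a 90% interval of 26% to 41% for 50/150.

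| 50/150 = 33.3% | 90% | 95% |
|---|---|---|
| Clopper-Pearson | 26.96% to 40.21% | 25.86% to 41.48% |
| Wald | 27.00% to 39.66% | 25.79% to 40.88% |
| Wilson | 27.35% to 39.91% | 26.29% to 41.21% |

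The printed figure does not reproduce at 90% by any of the three methods; at 95% all three round to it. This is a separate slip, but it means that the printed interval cannot serve as a check on a 90% table.

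For Arm B, I assume 13/75 = 17.3%, close to the 15/88 = 17.0% that the documents cite for nivolumab alone in PD-L1-positive subjects. The limits are 10.57% to 26.14% at 90% and 9.57% to 27.81% at 95%.

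**The case against.** The best defence is that listing only is deliberate and reasonable. Enrollment closed because no differential efficacy signal was seen, and the SAP restricts summary tables to Parts 1 and 2 in several sections. That explains the choice but does not document it. Where Revised Protocol 12 drops work, it says so, as it does for outcomes research, survival follow-up and submission of scans for central review. It left 8.2 and 8.4.2 in force for Part 3. What stands is that recording listing only, with a reason, would be as valid a remedy as adding the table.

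SAP 9 also refers to a Data Presentation Plan that is not available here. It may hold a Part 3 table, so what will finally be reported is unknown. That does not cure the SAP text.

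Four stronger readings are tempting, and the documents do not support them:

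- **The SAP defines ORR only on treated or response-evaluable subjects.** The bullet in 4.2.1.4 does, but the Part 3 text in the same section names the randomized combination arm, and 4.2.1.1 uses an unrestricted population of interest. The fault is inconsistency.
- **No interval level is stated.** Section 7.5 gives 95% in general, and 5.4 gives a two-sided 0.10 specifically for Part 3.
- **A planned comparison of arms is lost.** The visible protocol text asks for separate intervals, not a between-arm test.
- **The absence of Part 5 safety tables is a similar contradiction.** Protocol 8.4.3 asks for safety tables by arm or tumor type only where applicable, so adding them is a preference.

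**Conclusion.** The contradiction is real and rests on the text alone. The protocol requires Part 3 efficacy on the randomized set, with an ORR interval and summary tables for each arm. The SAP commits to none of these, conflicts with its own endpoint and sample-size sections, and does not record the departure. The size that follows from the documents is 0 of 2 required intervals. The widths, about 13 points for Arm A and 16 points for Arm B at 90%, are illustrations. They rest on planned sizes, on the protocol's example of 50 responders and on an assumed 13 responders in Arm B. If closure left smaller arms, the intervals would be wider at similar response rates. Lower precision calls for a descriptive label; it does not remove the requirement.

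**What to change.** 1. In SAP 7.1, add an exception to the listing rule: for Part 3, ORR is summarized for each randomized arm on All Randomized Subjects with a two-sided 90% Clopper-Pearson interval, the level that matches SAP 5.4, and is descriptive because enrollment closed early. A 95% interval may be shown beside it to match 7.5.
2. In SAP 6.3, make All Randomized Subjects the Part 3 efficacy population, and align the bulleted ORR definition in 4.2.1.4 with the Part 3 text there.
3. Reconcile who assesses response. Protocol 3.1.3 and SAP 2.1.3 make ORR by independent review primary. SAP 4.1 and 4.2.1.1 derive best response from investigator measurements, and scans need no longer be submitted for central review. State that the table uses investigator-derived response, and record this as a change from the independent-review endpoint.
4. If listing only is intended, record it in the SAP as a change from Protocol 8.2 and 8.4.2, with the reason.

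The cost is SAP wording and one table, built on best responses that 4.2.1.1 already derives for all Parts. The downside is a table with wide intervals that could be over-read without its descriptive label.

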7.2 Study Conduct

7.2.1 Study Information

A listing of batch number and randomization code (Part 3 only) will be provided.

Listing:

- Batch number
- Randomization code by site (include randomization codes, participant ID, treatment assigned)
 Part 3 only.

7.2.2 Accrual

The number (%) of participants accrued by country and investigational site will be summarized and listed, using All Enrolled population.

Summary:

• Number (%) of participants accrued by country and investigational site: Include country, site number, (Principal Investigator's name), number of participants enrolled, and number of participants treated

Listing:

• Participants accrued by country and investigational site.

7.2.3 Relevant Protocol Deviations

Non-programmable relevant eligibility and on-treatment protocol deviations, as well as significant (both programmable and non-programmable) will be reported through ClinSIGHT listings. The following programmable deviations from inclusion and exclusion criteria will be considered as relevant protocol deviations and a listing will be provided. The following programmable deviations from inclusion and exclusion criteria will be considered as relevant (i.e., protocol deviations that could potentially affect the interpretability of the study results).

At Entrance:

Subjects without measurable disease at baseline

Subject who received study medication less than 28 days from the last dose of the prior therapy

Subjects that have received greater than 5 prior treatment regimens

At Entrance for Expansion Cohorts:

Subjects with deviations on baseline or prior therapy related inclusion/exclusion criteria such as:

- NSCLC subjects:
 - who have not received prior platinum chemotherapy
 - with ALK translocation that have not received an ALK inhibitor
 - with an activating EGFR mutation that have not received an EGFR inhibitor
- Melanoma subjects:
 - who have not received prior therapy with ipilimumab
 - with BRAF mutation (V600E or V600K) present who have not received a RAF or MEK inhibitor.
- Colorectal Cancer (CRC) subjects:
 - without Microsatellite instability stable (no alterations) or microsatellite instability low (only one alteration)
 - without DNA mismatch repair gene proficient on tumor immunohistochemistry (IHC)
- Head and Neck Squamous Cell Carcinoma (SCCHN) (oral cavity, pharynx, larynx) subjects:
 - without evidence of progression or recurrence within six months of last dose of platinum therapy
 - with radiation therapy not completed at least 4 weeks prior to study drug administration
- Hepatocellular carcinoma (HCC) subjects
 - without Child-Pugh score of B
 - with hepatitis B infection with hepatitis B DNA viral load greater than 100 IU/mL and not on antiviral therapy
 - with hepatitis B infection with coinfection with hepatitis C or hepatitis D

On-treatment:

- Subjects receiving anti-cancer therapy while on study therapy
- Subjects treated differently than as assigned (subjects who received the wrong treatment for the entire study period, excluding the never treated)
- Subjects receiving greater than 10mg/day of prednisone or equivalent at the time of study drug administration.

7.3 Study Population

All study population related summary tables described in this section will include combined data from Part 1 and Part 2 only. Listings will include all available data from Parts 1, 2, 3, and 5.

7.3.1 Subject Disposition

Status of participants at the end of pre-treatment period will be summarized and listed by including all enrolled participants. Status of participants at the end of treatment period will be summarized by treatment and overall, based on All Treated population. In addition, status of participants at the end of each study period will be summarized as appropriate. A listing will be provided for those

participants who were treated and reason for discontinuation of treatment or not being followed will be described.

7.3.2 Demographic and Other Baseline Characteristics

Summary:

Descriptive statistics will be provided the following baseline characteristics for all treated participants by treatment and overall.

- Age at Consent (in years); Age Category ($<65, \geq 65$)
- Gender at Birth
- Race
- Ethnicity (if applicable)
- Height
- Weight
- ECOG PS
- Disease characteristics such as stage and severity of disease, mutation status, cell types, tumor locations (for SCCHN participants only), HPV status (for SCCHN participants only), prior cetuximab use (for SCCHN participants only), and prior therapy.

Listing:

All relevant data, generally variables listed above by treatment.

7.4 Extent of Exposure

The extent of exposure will be characterized according to the number of participants exposed, the duration of exposure, and the dose to which they were exposed. Analyses in this section will be performed on the All Treated Participants "as treated".

7.4.1 Study Therapy

Summary:

- Duration of therapy summary tables by treatment and total for each study drug: summarize by appropriate numbers of weeks intervals
- Dose information summary tables for each study drug: summary (mean, median, standard deviation, and min and max) of drug dosage, number of doses, duration of therapy, cumulative dose, dose intensity, and relative dose intensity.
 - Duration of therapy (weeks) is (last dose date first dose date +28)/7 for lirilumab, (last dose date first dose date +14)/7 for nivolumab, and (last dose date first dose date +42)/7 for ipilimumab (for Part 5 listing only).
 - Cumulative dose is the sum of all actual doses that a subject received.
 - Dose intensity is defined as the cumulative dose divided by the duration of treatment.
 - Relative dose intensity is defined as dose intensity divided by planned dose.

Listing:

- By patient listing of drug administered for each study drug by visit
- By patient listing of dosing information for each study drug: Duration of therapy, cumulative dose, dose intensity, and relative dose intensity by study drug.

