2.1.4 The Signal Detection Cohort Expansion (Part 4)

Removed with Revised Protocol 12.

2.1.5 The Signal Detection in SCCHN with Lirilumab, Nivolumab, and Ipilimumab Combination (Part 5 - closed to enrollment)

The Signal Detection in SCCHN with Lirilumab, Nivolumab, and Ipilimumab Combination (Part 5) is an open-label, Phase 2 cohort expansion study in subjects ≥ 18 years old with platinum-refractory recurrent or metastatic SCCHN that is not amenable to curative therapy evaluating lirilumab in combination with nivolumab and ipilimumab as a treatment. There will be continuous monitoring of safety via a safety lead-in, described in detail later in this section. Subjects must have tumor progression or recurrence after prior platinum-containing systemic therapy for recurrent or metastatic disease. In addition, subjects who have progressed within 6 months of platinum-based therapy used as part of concurrent chemoradiation (definitive or adjuvant therapy) are also eligible.

All subjects in this cohort with be tested for PD-L1 status. All testing for PD-L1 status will be performed on a fresh biopsy obtained during screening, and results must be available prior to randomization. In the event that the biopsy sample collected during screening is not evaluable for PD-L1, the site will be notified and an archival specimen may be submitted for PD-L1 testing. Additional subjects may be enrolled, if necessary, to ensure an adequate representation of the patient population (ie, non-, lower-, and higher-PD-L1 expressers).

screening evaluations to determine eligibility within 35 days prior to enrollment.

Subjects will be treated with lirilumab, nivolumab, and ipilimumab combination (see Table 5.1.4-2 of the protocol for dosing schedule) as follows:

- Nivolumab 3 mg/kg IV Q2W (± 3 days)
- Ipilimumab 1 mg/kg IV Q6W (± 3 days) following the administration of nivolumab
- Lirilumab 3 mg/kg IV Q4W (± 3 days) will be the final drug administered on any specific treatment day

Approximately 40 subjects will be enrolled.

The total duration of the study from enrollment to primary endpoint ORR analysis is expected to be approximately 21 months, assuming 12 to 15 months accrual duration.

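### Relative dose intensity divides a dose per week by a dose per administration, so a fully compliant subject scores 25% for lirilumab, 50% for nivolumab and 17% for ipilimumab

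*SAP*

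**What the plan says.** SAP 7.4.1 (Study Therapy) builds the exposure measures in four steps.

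- **Duration.** For lirilumab: "Duration of therapy (weeks) is (last dose date first dose date +28)/7 for lirilumab". The nivolumab and ipilimumab versions add 14 and 42 days instead of 28. (The minus sign between the two dates is lost in the text as read; the meaning is clear.) The ipilimumab version is marked for the Part 5 listing only.
- **Cumulative dose.** "Cumulative dose is the sum of all actual doses that a subject received".
- **Dose intensity.** "Dose intensity is defined as the cumulative dose divided by the duration of treatment".
- **Relative dose intensity.** "Relative dose intensity is defined as dose intensity divided by planned dose".

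The SAP does not define planned dose, and it mentions neither a planned dose per week nor a planned dose intensity. Elsewhere the documents state planned treatment as an amount per administration plus an interval, for example "Lirilumab 3 mg/kg IV Q4W" in the Part 5 description.

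Relative dose intensity is to be summarised for each study drug and listed by patient. Under SAP 7.1, the summaries combine Parts 1 and 2, and Parts 3 and 5 appear in listings only.

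**The concern.** The numerator and denominator are in different units. Dose intensity is an amount per week. Planned dose, as the documents use doses, is an amount. Their ratio is therefore in 1/week and is not a proportion of the planned intensity. Its maximum for on-schedule dosing depends on the dosing interval, so each drug has a different ceiling, and none is 100%.

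This matters because relative dose intensity is the one listed exposure measure that sets the amount delivered against the amount planned. Dose reductions are not permitted (Protocol 4.9.2), so shortfalls arise mainly from delays and omissions, and SAP 7.4.2 only counts subjects with those events. Safety and tolerability are the primary objective in Part 1, and safety is part of the primary objective in Part 2 (SAP 3.1.1). Readers of those results will want to know how much of the planned drug was given.

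**Working it through.** The documents give no numerical relative dose intensity, so there is no planned figure to reproduce. The check applies the SAP formulas to a subject who receives every dose in full and on time.

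**Inputs**

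- Duration, cumulative dose, dose intensity and relative dose intensity: SAP 7.4.1.
- Lirilumab 3 mg/kg every 4 weeks, nivolumab 3 mg/kg every 2 weeks, ipilimumab 1 mg/kg every 6 weeks: SAP 2.1.5. Parts 1 and 2 use the same lirilumab and nivolumab intervals, with four nivolumab and two lirilumab doses per 8-week cycle (SAP 2.1.1 and 2.1.2).

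**General result.** Let a subject receive n full doses of size D, exactly I days apart.

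- Duration = ((n − 1)I + I)/7 = nI/7 weeks.
- Dose intensity = nD ÷ (nI/7) = 7D/I per week.
- Relative dose intensity as written = (7D/I) ÷ D = 7/I.

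The answer depends on neither the dose nor the number of doses, only on the interval.

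**A compliant 24-week course**

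| Drug | Doses | Cumulative (mg/kg) | Dose intensity (mg/kg/week) | As written | Against planned dose per week |
|---|---|---|---|---|---|
| Lirilumab 3 mg/kg, I = 28 | 6 | 18 | 18/24 = 0.75 | 0.75/3 = 25% | 0.75/(3/4) = 100% |
| Nivolumab 3 mg/kg, I = 14 | 12 | 36 | 36/24 = 1.5 | 1.5/3 = 50% | 1.5/(3/2) = 100% |
| Ipilimumab 1 mg/kg, I = 42 | 4 | 4 | 4/24 = 0.167 | 0.167/1 = 16.7% | 0.167/(1/6) = 100% |

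The percentages are the same from a single dose up to 96 weeks of dosing. They are also the same at lirilumab 0.1 mg/kg (25%) and at the flat 240 mg doses of lirilumab (25%) and nivolumab (50%).

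**Could planned dose mean something else?** If it meant the planned cumulative dose, the ratio would be (7D/I)/(nD) = 7/(nI), which shrinks with time on treatment. A compliant lirilumab subject would score 25% after one dose and 7/(24 × 28) = 1.04% after 24 doses. Of the three readings tested, only planned dose per week returns 100%.

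**Comparison between drugs.** A nivolumab subject given half the planned amount over 24 weeks receives 18 mg/kg. That is 18/24 = 0.75 mg/kg/week, and 0.75/3 = 25%: the same score as a fully compliant lirilumab subject.

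**The case against.** The SAP never says that planned dose means dose per administration; that is an interpretation. Planned treatment is always stated with its interval, so the authors and programmers may well intend planned dose per week. SAP 9 places the full list of analyses in a Data Presentation Plan that is not among these documents, and the derivation might be spelled out there.

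The consequences are also limited. Within one drug the literal result is the intended one multiplied by a constant (1/4, 1/2 or 1/6), so the ordering of subjects and dose groups is preserved and the intended value can be recovered. A ceiling at exactly 25% or 50% would probably be noticed when the outputs are checked. The same tables report number of doses, duration, cumulative dose and dose intensity, all unaffected, and SAP 7.4.2 summarises delays, omissions and discontinuations. The response endpoint, the adverse event rates and the dose-proportionality model do not use relative dose intensity. The SAP sets no threshold for it.

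The points about reach stand, and they keep this from being a serious defect. The point about interpretation does not remove the error. Section 7.4.1 uses cumulative dose and dose intensity as separate terms, so planned dose does not plainly mean planned dose intensity, and any reading of it as an amount leaves a ratio in 1/week. The intended formula is probably the conventional one: the 28, 14 and 42 days added to duration are exactly what makes compliant dosing equal 100% against a weekly plan. The SAP does not say so.

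**Conclusion.** The definition is wrong as written. With planned dose read as the dose per administration, the natural reading, perfect compliance scores 25% for lirilumab, 50% for nivolumab and 16.7% for ipilimumab instead of 100%. The understatement is a factor of 4, 2 and 6 respectively, whatever the dose level or time on treatment.

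The lirilumab and nivolumab errors would reach the Part 1 and 2 summary tables and the by-patient listings. The ipilimumab error is confined to the Part 5 listing. No primary endpoint or inference changes. It should be corrected before the exposure outputs are programmed. Whether the wrong values would actually be produced depends on how the programmers interpret the sentence, which the documents do not settle.

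**What to change.** Replace the last definition in SAP 7.4.1 with: relative dose intensity (%) = 100 × dose intensity ÷ planned dose intensity, where planned dose intensity is the assigned dose per administration divided by the planned interval in weeks (4 for lirilumab, 2 for nivolumab, 6 for ipilimumab). In the same place, state whether cumulative dose is in mg or mg/kg for the weight-based regimens, so that numerator and denominator use the same unit.

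The cost is one SAP sentence and one derivation line in the exposure dataset. No new data are needed, and no dose, schedule or clinical rule changes.
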